## **o Methods**

**Study Design:** This study will use a pilot randomized control trial to test the effectiveness of a self-screening process with older adults. The hypothesis is that older adults exposed to the self-screening process will follow up with health professionals to receive help for the UI condition. There will be two groups of older adults. The intervention group will participate in self-screening and the control will not be exposed to self-screening. Using this approach is necessary to determine whether or not the self-screening works.

*Intervention:* The intervention will include a combination of self-screening and UI specific information and resources. Older adults in the intervention group will complete a gender specific UI Self-Screening tool. Men will complete the International Consultation on Incontinence Modular Questionnaire (ICIQ) for Males  (**See ICIQ-M**) and women will complete the ICIQ for Females. (**See ICIQ-F**). The ICIQ Male and Female are valid and reliable tools, recognized by the International Continence Society, and collect more information about urinary symptoms than other tools, an advantage for referral purposes. In addition, the intervention group will receive a fact sheet with UI specific information, contact information to the local incontinence clinic and a link to a website with patient incontinence resources and education (**See UI Fact Sheet**).

*Control Group:* Older adults assigned to the control group will receive standard care from their physicians. Standard care may differ from general practitioner to general practitioner. Usual care for urinary incontinence (UI) from general practitioners is generally minimal. Most patients do not tell their physicians about UI, and most physicians do not ask about UI. If this topic does come up during a GP appointment, a patient may be offered no treatment, lifestyle advice (e.g., do not drink before bed), told to do Kegels (but likely not instructed how to do these properly) or in some cases, offered pharmacological therapies (which will be captured in our questionnaire with the participants). But standard of care is unfortunately very often no care.

**Setting:** Senior's Centers and organizations dedicated to seniors in Kelowna, West Kelowna and Lake Country will serve as the recruitment sites for this study. These Senior's Centers/organizations (e.g., Lake Country Seniors Centre, Lake Country

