### **Data Collection:**

*Pre-test:* Prior to implementation, the self-screening tool will be pre-tested with 5 older adults attending participating seniors centres/organizations. The purpose of the pretest will be to identify any implementation issues such as recruitment, administration, understanding and ease of use of the self-screening tools.

*Procedures:* Older adults assigned to both groups will receive follow up from the RA who will provide details about the study and answer any questions. Prior to randomization, consenting older adults from both groups will complete a demographic (e.g., age, sex, highest level of education, household income), health history profile (e.g., co-morbidities, history of previous referrals for UI, medications) (**see Demographic and Health History Profile**) and a quality of life questionnaire (**see The King's Health Questionnaire**).

Three months following study entry participants from both groups will receive a phone follow-up to obtain information about actions they have taken re IU (e.g., self/physician

referral), UI symptoms,  treatments received, satisfaction with care (**See Three Month Follow up Questionnaire**), and changes in quality of life. The follow up phone call will be recorded. It is expected the baseline and 3 month follow up data collection will take approximately 20-30 minutes to complete.

The primary outcome will be the numbers of older adults who take action to receive help for their UI during the 3-month follow-up from study entry: self-referral to the local UI clinic, appointment with GP about their UI, and/or referral to a specialist (urologist or urogynecologist or gynecologist), or other action. Secondary outcomes will include: treatments received, satisfaction with care, changes in quality of life.

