#### *Primary analysis:*

The study hypothesis is that older adults exposed to the self-screening process will follow-up with health professionals to receive help for their UI condition more often than the control group. To test this hypothesis, investigators will calculate the proportion (with 95% CI) of participants who self-report as having self-referred to a health professional (binary yes/no response) during the study period for each group. A chi-square test will be conducted to determine if the self-screening process is associated with self-referral to a health professional. In addition, a logistic regression analysis will be conducted to model the odds of self-referring among people who have undergone self-screening, adjusting for demographics, and health history variables. Bivariate analysis will be conducted and variables significantly associated with self-referral will be entered into the model. Since the study sample size will only allow for having 3 variables in the

model, more than one regression model may be necessary. If this is the case, a Bonferroni adjustment will be used to account for multiple comparisons.

*Secondary analysis:*

Quality of life scores will be compared within and between groups. For the within group comparison a two-sided dependent t-test will be conducted using the pre-study and 3-month quality of life scores for each group. To determine if a change in quality of life (difference between pre-study and 3-month quality of life scores) is statistically significant and mixed between-within subjects analysis of variance will be conducted.

All participants will complete a Urinary Symptoms questionnaire (ICIQ-FLUTS) which consists of ordinal categorical responses to questions related to urinary symptoms. Each question has five response options. For each question, each response category will be assigned a numeric value depending on the severity of the symptom (1= no symptoms; 5=severe symptoms). For each participant, improvement in symptoms will be determined by a reduction in the ordinal value. Improvement in UI symptoms will be compared between groups using a chi-square test.

Investigators are also interested in knowing if self-screening results in a higher proportion of participants initiating medication of UI during the study period. Therefore, the proportion of participants in each group who started medication for UI during the study period will be compared using a chi-square test.

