**Limitations:** It is possible that screening for eligibility for the study may make a person more likely to self-refer. If this occurs in the control arm, it may bias the results toward the null hypothesis (i.e. it may be less likely to detect a difference between study arms).

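### The primary event is an uncorroborated yes/no self-report in a trial where participants can tell their arm, so reporting may differ by arm in the hypothesis's favour, and the Limitations section names only a bias toward the null.

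*Combined protocol and SAP*

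**What the plan says.** - **Event analysed.** Under Data Analysis, Primary analysis, each group's proportion is of participants who "self-report as having self-referred to a health professional (binary yes/no response) during the study period". The groups are compared by chi-square test, and the logistic regression models the same self-referral outcome.
- **Outcome as defined.** Data Collection words it more broadly: "The primary outcome will be the numbers of older adults who take action to receive help for their UI during the 3-month follow-up from study" (that is, from when the participant joins). Its list of qualifying routes ends with "referral to a specialist (urologist or urogynecologist or gynecologist), or other action". The last item is not defined.
- **Source.** At three months "participants from both groups will receive a phone follow-up to obtain information about actions they have taken". The same call covers symptoms, "treatments received, satisfaction with care" and quality of life, and "The follow up phone call will be recorded". No confirmation from any provider is described.
- **What differs by arm.** Under Methods, Intervention, only the intervention arm completes the screening tool and receives the fact sheet and "contact information to the local incontinence clinic". Controls receive standard care.
- **Masking.** None is described. Sampling and Recruitment has the research assistant open the envelope that reveals the arm after consent.
- **Acknowledged bias.** Limitations covers one mechanism: eligibility screening may prompt controls to self-refer, in which case "it may bias the results toward the null hypothesis".

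**The concern.** The outcome is the participant's own answer. A person who was screened and handed a clinic's details, and is then asked whether they sought help, may feel a pull to say yes that a control does not feel, or feels less. If over-reporting differs in that way, the trial shows an effect where none exists, in the direction it hopes for. Masking the caller would not cure this, because the error lies in the answer and not in how it is recorded. Equal over-reporting in both arms would do far less harm; the difference between arms is what matters.

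With 12 per arm, a very few answers decide significance. A reader of Limitations would also learn of a bias in one direction only.

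**Working it through.** **The plan's own figure.** Inputs from Sampling and Recruitment: 14% self-referral without intervention, a 61% increase (read as percentage points, so 75%), 80% power, p < .05 (two-sided assumed), 12 per arm.

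n = [1.96·√(2·0.445·0.555) + 0.842·√(0.14·0.86 + 0.75·0.25)]² / 0.61² = (1.378 + 0.467)² / 0.372 ≈ 9.1, so 10 per arm. With continuity correction it is about 12.2, so 13. The stated 12 lies between. Exact power at 12 per arm is 92% by uncorrected chi-square and 83% by Fisher's test. The planned number is therefore consistent with 14% versus 75%.

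**How few answers matter.** With 2/12 events in controls, 6/12 in the intervention arm gives χ² = 3.00 (p = 0.083) and 7/12 gives χ² = 4.44 (p = 0.035). One answer moves the result across the threshold. Fisher's test needs 8/12.

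**False positives under differential reporting.** Assume a true rate of 14% in both arms (no effect), and that a share f of those who took no action answer yes. Then

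reported rate = 0.14 + 0.86 × f.

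For f = 20%: 0.14 + 0.86 × 0.20 = 0.312. At 12 per arm that is 12 × 0.86 × 0.20 ≈ 2 false yes answers. The probability of p < .05 is the sum of the two binomial probabilities over every pair of counts that the test calls significant. The shares f are assumptions, since the documents give none.

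| Over-reporting, intervention vs control | Reported rates | Chi-square, 12/arm | Fisher, 12/arm | Chi-square, 18/arm |
|---|---|---|---|---|
| 0 vs 0 | 14.0% vs 14.0% | 2.7% | 0.6% | 4.5% |
| 10% vs 0 | 22.6% vs 14.0% | 6.3% | 2.2% | 9.6% |
| 20% vs 10% | 31.2% vs 22.6% | 7.0% | 2.8% | 8.5% |
| 20% vs 0 | 31.2% vs 14.0% | 15.0% | 7.0% | 22.4% |
| 30% vs 5% | 39.8% vs 18.3% | 20.6% | 10.6% | 29.3% |

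Chi-square here is uncorrected; the plan does not say whether a correction applies. Twelve per arm is the plan's required number, and 18 per arm means that all 36 recruits are followed. If half of the 36 drop out, 9 per arm remain, and 20% vs 0 takes the chi-square rate from 1.7% to 12.3%.

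Equal over-reporting of 20% in both arms gives 5.0% at 12 per arm. So part of the rise in the 20% vs 10% row comes from higher rates making the test less conservative, and only the rest from the difference between arms.

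**Upper bound on what misreporting explains.** To turn 14% into 75% by false answers alone, f would have to be 0.61 / 0.86 = 71% of intervention non-actors.

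**The case against.** Self-report is a defensible choice for a 36-person pilot that counts contacts across a clinic, GPs and several specialties. Several stronger readings are also tempting, and the documents do not support them.

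- *That intentions count as events.* Both sections describe completed acts: having self-referred, and actions taken. A plan to call is not an event as defined. What stands is that the plan has no explicit rule excluding intentions and leaves the final catch-all action undefined.
- *That the call asks nothing but yes or no.* The binary wording describes the analysed variable. The recorded call also asks about type of action and treatments, and the Three Month Follow up Questionnaire is not in the text, so provider and date items may already exist. What stands is that these too are self-report, and Primary analysis gives no rule for using them.
- *That the pull to say yes falls on one arm only.* This is not shown. Controls have symptoms, consent, complete the same baseline forms and receive the same call, so they may over-report too. The 20% vs 10% row shows how much that shrinks the problem.
- *That a positive result would be presented as conservative.* Limitations is conditional and says nothing about how a positive result would be described. What stands is that bias in the other direction is missing.

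Providing contact details is also part of the intervention and a legitimate route to a real effect. The objection is to reporting that may differ by arm, not to the handout.

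**Conclusion.** The concern holds as a risk of unknown size. The facts are in the plan: a self-reported event, no described corroboration, an allocation that participants can see, clinic details given to one arm, and a limitation stated in one direction only. That participants are unmasked is inferred from the design, since the plan does not discuss masking.

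At 12 per arm with no true effect, the assumed patterns from 10% vs 0 to 20% vs 0 put the false-positive rate at 6.3% to 15.0% by uncorrected chi-square, against 2.7% without over-reporting. By Fisher's test they put it at 2.2% to 7.0%, against 0.6%. At 18 per arm the chi-square rate goes from 4.5% to 22.4% for 20% vs 0. These figures rest on assumed over-reporting shares and a 14% true rate in both arms. Modest misreporting could not plausibly create the hypothesised 61-point gap, but it could create a smaller significant one. A cheap tightening of the event definition is worthwhile; the finding does not invalidate the design.

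**What to change.** 1. **Primary analysis.** Count an event only when the participant reports a completed contact and names the type of provider or clinic and an approximate date within the 3-month window. Ask this identically in both arms on the recorded call, using existing questionnaire items if they are there. State that plans do not count.
2. **Data Collection.** State what the catch-all final action covers.
3. **Sensitivity analysis.** Keep the plain yes/no answer as a sensitivity analysis.
4. **Clinic confirmation.** If participants consent, ask the local clinic for a yes/no confirmation of reported clinic contacts in both arms, as a supportive check only. It must not be required for an event. It cannot confirm GP or specialist contacts, and because that clinic was advertised to one arm, requiring it would make intervention events easier to verify than control events.
5. **Limitations.** Add that differential self-report may bias the result away from the null.

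The cost is up to two call items, analysis-plan wording and, if step 4 is used, a consent line and a short list for the clinic to answer. A few true contacts that cannot be dated will be lost, which matters in participants aged 65 and over. The stricter event is still self-report: a courtesy yes becomes harder to count, but the bias is reduced and not removed.

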Health Planning Society, Westside Health Network, Seniors Outreach Bureau) serve large and different populations of seniors (>300 seniors) so overlap in membership is not expected to be an issue.

**Sampling and Recruitment:** The study sample will include older adults  $\geq 65$  years of age (men and women) who attend a local Senior's Centre or organization, report having some UI symptoms, are independent living, ambulatory, with no more than mild cognitive impairment, able to read and write in English or have someone who can assist with reading the data collection information and can complete a paper survey independently. Older adults will be excluded if they have cognitive impairment, require more than minimal assistance with completing the survey, or have any impairment (e.g., vision) that would make self-screening and follow up challenging. They must also never have been referred to a UI specialist or program in the past.

Following ethics approval, eligible older adults will be recruited through a letter of invitation sent through e-mail distribution lists of our participating seniors centres/organizations (**see Letter of Invitation**). Based on other UI studies, in which there was a 14% self-referral rate without an intervention, we hypothesize a 61% incremental increase in self-referral in the arm receiving the intervention. The sample size required to detect an improvement in self-referral (with 80% power,  $p < .05$ ) to a health professional (e.g., UI specialist) is 24 participants (12 older adults per arm). Drop-out or attrition is common in research studies. In factoring the potential for a drop-out rate of 50%, a sample size of 36 participants will be recruited. Excel randomization function will be used to assign participants to one of the two arms (the arm receiving the self-screening process or the arm not receiving this process). The randomization assignments (allocations) will be placed in individual sealed envelopes. After informed consent is obtained, the Research Assistant (RA) will choose the next available envelope to reveal which arm the study participant will be assigned.

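### The supportive logistic model has no fallback for small arms in which no finite odds ratio exists, and it picks its covariates from the outcome data

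*Combined protocol and SAP*

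**What the plan says.** Under Data Analysis, Primary analysis, the hypothesis is tested by a chi-square comparison of self-referral between arms, reported with per-arm proportions and 95% CIs. A logistic regression is then added to model "the odds of self-referring among people who have undergone self-screening, adjusting for demographics, and health history variables". Covariates are chosen as follows: "Bivariate analysis will be conducted and variables significantly associated with self-referral will be entered into the model". The plan continues "Since the study sample size will only allow for having 3 variables in the" model, so several models may be fitted. In that case "a Bonferroni adjustment will be used to account for multiple comparisons".

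The plan gives no covariate list, no significance threshold for entry, and no statement on whether study arm counts among the 3 variables. It names no method for the case where an ordinary fit has no finite estimate.

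The planning figures are in Methods, Sampling and Recruitment: 14% self-referral without intervention, and "we hypothesize a 61% incremental increase in self-referral in the arm receiving the intervention". At 80% power and p < .05 the stated requirement is 24 participants, 12 per arm. On attrition the plan says: "In factoring the potential for a drop-out rate of 50%, a sample size of 36 participants will be recruited".

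**The concern.** A logistic model has no finite maximum-likelihood odds ratio for study arm when nobody, or everybody, in one arm has the event. With a 14% control rate and arms of this size, a control arm with no self-referrals is a realistic result. The planned adjusted odds ratio then cannot be reported from an ordinary fit, and someone must choose another method after seeing the outcomes.

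There is a second, smaller matter. When covariates are chosen by their association with the outcome in the same small sample, unrelated variables enter by chance and the model is not fixed in advance. The Bonferroni provision addresses neither issue.

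This is the only adjusted effect estimate planned, and it sits under the primary analysis heading, although the chi-square test carries the hypothesis.

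**Working it through.** **Which rates does the sample size imply?** The 61% figure can be read in more than one way. Per-arm sizes for 80% power and a two-sided 5% test, without / with continuity correction, are:
- 14% vs 75% (61 percentage points added): 9.1 / 12.2
- 14% vs 61%: 15.4 / 19.4
- 14% vs 22.5% (61% relative increase): 320 / 343

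Exact two-sided Fisher power for 14% vs 75% is 75.9% at 11 per arm and 83.2% at 12, so this reading reproduces 12 per arm. The plan does not state sidedness. A one-sided 5% test of 14% vs 61% gives 12.03 per arm without correction, and about 84% exact power at 12. I use 75% as the main case and 61% as a check.

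**Numbers analysed.** Three cases, taking equal arms: 18 per arm (36 recruited, no loss), 12 per arm (the stated requirement) and 9 per arm (36 × 0.5 = 18 left in total).

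**Expected events**, n × (0.14 + 0.75):
- n = 9: 8.0, or 2.7 per variable for 3 variables
- n = 12: 10.7, or 3.6
- n = 18: 16.0, or 5.3

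**Chance of no finite treatment odds ratio, arm alone.** This is the probability that either arm has no events or all events:

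1 − (1 − (1−p₀)ⁿ − p₀ⁿ)(1 − p₁ⁿ − (1−p₁)ⁿ)

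| Control vs intervention rate | 9 per arm | 12 per arm | 18 per arm |
|---|---|---|---|
| 14% vs 75% | 31% | 19% | 7% |
| 14% vs 61% | 27% | 17% | 7% |
| 30% (assumed) vs 75% | 11% | 4.5% | 0.7% |

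For 14% vs 75% at n = 12, 0.86¹² = 0.164 and 0.75¹² = 0.032, and the other two terms are negligible. The result is 1 − 0.836 × 0.968 = 0.19. Most of the risk is a control arm with no events, which alone has probability 25.7%, 16.4% and 6.6% at 9, 12 and 18 per arm.

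**With the selection rule.** This was simulated at 14% vs 75%, assuming six unrelated candidates, entry at p < 0.05, arm always kept and at most two covariates. A fit counts as failed if any coefficient lacks a finite estimate. Failure rates are about 37-39%, 23-28% and 9% at 9, 12 and 18 per arm. The range reflects covariate type, and simulation error moves the figures by a few points.
- At least one unrelated covariate enters in about 27-31% of trials.
- Across all trials, the adjusted odds ratio differs from the unadjusted one by more than 1.5-fold in about 5-9%, and by more than 2-fold in about 2-5%.
- Wald 95% CI coverage among finite fits is 96-98%.

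**Does naming covariates in advance cure the failure?** No. Ordinary fits at 12 per arm with unrelated binary covariates forced in fail in about 28% of trials with one covariate and 37% with two. That is no better than the selection rule.

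**Does a Firth fit cure it?** Yes. At 14% vs 75% the true log odds ratio is ln[(0.75/0.25)/(0.14/0.86)] = 2.91. In 2,400 simulated trials per size, with one or two binary covariates, the estimate was finite every time. Mean log odds ratios were 2.82 to 2.96, and profile-likelihood coverage was 95.5% to 97.5%.

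**The case against.** The strongest reply is that this is a pilot, the model is supportive, and the chi-square test and proportions can be reported whatever happens to the regression. That stands, and it sets the priority.

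The larger percentages also depend on unfavourable conditions. The 31% figure needs the full 50% drop-out. The control rate may exceed 14%: Limitations expects that eligibility screening could prompt self-referral, and Data Collection defines the primary outcome more broadly, counting GP appointments, specialist referrals and other actions. Both points stand, so the 7% at 18 per arm and the lower figures at a 30% control rate belong beside the headline.

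Three stronger inferences are tempting and are not supported.
- A reader might conclude that 75% is the only rate compatible with 24 participants. It is not, because a one-sided test of 14% vs 61% also gives about 12 per arm. The conclusion changes little.
- A reader might take the phrase about people who have undergone self-screening to mean that only the intervention arm is modelled. The sentence follows a between-arm test and speaks of adjustment, so both arms are almost certainly meant. The wording needs clarifying, and no figure should rest on the one-arm reading.
- A reader might blame the selection rule for the failures, or infer that it distorts the odds ratio. Most of the failure risk is present with arm alone, and chance-selected covariates seldom move the estimate much.

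**Conclusion.** The concern holds as a low-priority improvement. The plan has no provision for a fit without a finite odds ratio. At 14% vs 75% that occurs in 31%, 19% and 7% of trials at 9, 12 and 18 analysed per arm with arm alone, and somewhat more often once covariates enter. The result hardly depends on whether the intervention rate is 75% or 61%. It depends strongly on the control rate, as the 30% case shows.

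Outcome-driven selection is a separate and lesser weakness: it makes the model unpredictable but has little effect on the odds ratio. The covariate results rest on assumptions about the number and type of candidates, the entry threshold and the retention of arm, because the plan specifies none of these.

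None of this undermines the trial's main comparison, which does not use the model.

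**What to change.** Replace the sentences on the logistic model, bivariate screening, multiple models and Bonferroni with wording such as:

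*One supportive logistic model will compare the two study arms. Study arm will always be included, with one (at most two) baseline covariates named before outcome data are reviewed. The model will be fitted by Firth penalised likelihood with a profile-likelihood 95% CI. The chi-square comparison remains the test of the hypothesis. Other covariates will be tabulated by self-referral status.*

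The Firth fit is what makes the odds ratio always reportable. Naming covariates in advance removes data-driven selection but does not itself prevent failure of an ordinary fit. Saying that both arms are compared also settles the ambiguous phrase.

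The choice of covariate is the investigators'. History of previous UI referrals would be a poor one, because eligibility largely fixes it: "They must also never have been referred to a UI specialist or program in the past".

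The cost is a paragraph of SAP text and a standard software option, with no new data. The downside is that fewer covariate associations are explored by modelling.

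### Change in quality of life is compared between arms only by a mixed ANOVA with no term or estimate named; ANCOVA on the baseline score already collected is usually more precise

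*Combined protocol and SAP*

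**What the plan says.** Data Collection lists change in quality of life among the secondary outcomes: "Secondary outcomes will include: treatments received, satisfaction with care, changes in quality of life". The King's Health Questionnaire is completed by both arms before allocation ("Prior to randomization, consenting older adults from both groups will complete a demographic" profile, a health history "and a quality of life questionnaire") and again at the 3-month telephone call.

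The analysis is under Data Analysis, Secondary analysis. It opens with "Quality of life scores will be compared within and between groups". The within-group part is a two-sided paired t-test in each arm. The between-group part rests on one sentence, which describes change as the "difference between pre-study and 3-month quality of life scores" and ends "statistically significant and mixed between-within subjects analysis of variance will be conducted".

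That sentence does not say which term of the ANOVA is the test of interest, and it names no between-arm estimate or confidence interval. No other section adjusts a quality-of-life score for its baseline. The only adjusted model in the plan is the logistic regression for self-referral. Description of Sample covers summaries in total and by group, which are not an estimate of the difference between arms.

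**The concern.** There are two linked points.

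**The term is open.** A two-visit mixed ANOVA gives three tests: group, time and group-by-time. The plan's description of change makes group-by-time the natural reading, but it is not stated. The others answer different questions. The time effect does not compare arms. The group effect averages a score taken before randomisation with one taken after it, so it estimates only half of the 3-month difference.

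**The natural reading usually gives up precision.** Group-by-time is a change-score analysis, which fixes the slope of 3-month on baseline score at 1. ANCOVA estimates that slope and usually leaves less residual variance. The baseline score it needs is already collected.

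What is at stake is the width of the interval, not bias. The Study Design paragraph says "This study will use a pilot randomized control trial", and Sampling and Recruitment says "In factoring the potential for a drop-out rate of 50%, a sample size of 36 participants will be recruited". With so few complete pairs the quality-of-life estimate will be imprecise under either method, so precision that needs no extra data is worth having. A pilot also has more use for an estimate and interval than for a p-value. The paired t-tests are correctly described as within-group comparisons and are not part of this point.

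**Working it through.** **Inputs from the documents.** There is one baseline score before randomisation and one score at 3 months, in two arms. The plan gives no sample size or precision figure for quality of life, so there is none to reproduce; its target of 24 (12 per arm) was set for self-referral. Let N be the number with both scores. I used N = 18 (half of 36 lost: 36 × 0.5), N = 24 (the sample-size target) and N = 36 (no loss).

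**Assumptions.** The documents give neither the SDs nor the baseline to 3-month correlation ρ. I set the baseline SD to 1 and the 3-month SD to k = 1, 1.25 or 0.8, with ρ = 0.3, 0.5 or 0.7. I also assumed equal arms, complete pairs, normal scores, and the same SDs and ρ in both arms.

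**Step 1: what the mixed ANOVA tests.** With two visits and complete pairs, the group-by-time F equals the squared t from a two-sample test on change scores. A check on a simulated data set of 24 gave 1.860 for both.

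**Step 2: variances of the between-arm difference.**

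- Change score: (1 + k² − 2ρk) × 4/N, with N − 2 degrees of freedom.
- ANCOVA: k²(1 − ρ²) × (4/N) × (1 + 1/(N − 4)), with N − 3 degrees of freedom. The last factor is the price of estimating the slope.

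Before that factor, the change-score variance exceeds the ANCOVA variance by (1 − ρk)² × 4/N. This is never negative, and it is zero only when the true slope ρk is 1.

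**Step 3: one case in full (N = 24, k = 1, ρ = 0.5).**

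- Change score: variance 1.00 × 4/24 = 0.1667, SE 0.408, t(22) = 2.074, half-width 0.85 SD.
- ANCOVA: variance 0.75 × 0.1667 × 1.05 = 0.1313, SE 0.362, t(21) = 2.080, half-width 0.75 SD.
- Width ratio 0.890, so the interval is 11% narrower.

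At the same N and ρ, the half-width goes from 0.97 to 0.94 if k = 1.25, and from 0.78 to 0.60 if k = 0.8 (in baseline SDs).

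**Step 4: CI-width ratio, ANCOVA divided by change score (below 1 favours ANCOVA).**

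| k | N | ρ = 0.3 | ρ = 0.5 | ρ = 0.7 |
|---|---|---|---|---|
| 1 | 18 | 0.839 | 0.901 | 0.960 |
| 1 | 24 | 0.828 | 0.890 | 0.947 |
| 1 | 36 | 0.820 | 0.880 | 0.937 |
| 1.25 | 18 | 0.922 | 0.983 | 1.031 |
| 1.25 | 24 | 0.910 | 0.971 | 1.018 |
| 1.25 | 36 | 0.900 | 0.961 | 1.007 |
| 0.8 | 18 | 0.737 | 0.787 | 0.825 |
| 0.8 | 24 | 0.728 | 0.777 | 0.814 |
| 0.8 | 36 | 0.720 | 0.769 | 0.805 |

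Simulation of these 27 settings, with 40,000 trials each, agreed with the formula to within about 0.003. Type I error was 0.048 to 0.052 for both methods.

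**Step 5: where ANCOVA loses.** With equal SDs it is wider above ρ of about 0.85, 0.89 and 0.935 (N = 18, 24, 36). With k = 1.25 it is wider for ρ between about 0.56 and 0.92, 0.61 and 0.90, and 0.66 and 0.89. The worst case is a true slope of 1, where the ratio is √(1 + 1/(N − 4)) × t(N − 3)/t(N − 2) = 1.041, 1.028 and 1.017.

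**Step 6: why the term needs a name.** With 12 per arm, ρ = 0.5, equal SDs and an assumed difference of 0.8 SD at 3 months, simulated power was 19% for the group term, 46% for group-by-time and 56% for ANCOVA. The group term estimated 0.40 SD on average.

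**The case against.** The strongest reply is that this is a choice between two valid methods. The group-by-time test is unbiased under randomisation and matches the outcome as the protocol names it. The within-group comparison is already assigned to the paired t-tests, so group-by-time is the only sensible reading and an analyst is unlikely to report another term. The gain depends on figures the documents do not give, and its direction can change. With a 3-month SD 1.5 times baseline and ρ = 0.5, ANCOVA is 2% wider, 1% wider or level (N = 18, 24, 36); at ρ = 0.7 it is 2 to 4% wider. Such settings are not far-fetched. If controls mostly receive no care, their scores may be stable and ρ high; if only some of the intervention arm seek help, 3-month scores may spread out, and perhaps in that arm only. Quality of life is also a secondary outcome of a pilot, and no stated decision depends on it.

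Most of this is right, and it limits the size of the point. The test is valid, the gain is modest and uncertain, and the missing label alone would be a small matter. But it does not remove the point. The possible loss is capped at about 4% at N = 18, while with equal SDs the gains run from 4 to 18% over the range shown. Raising the 3-month SD by 40% in one arm only left type I error near 5% for both methods, with width ratios from about 0.9 to 1.02. The missing between-arm estimate also remains, whichever method is preferred.

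**Conclusion.** The concern holds. The only planned between-arm analysis of change in quality of life is a mixed ANOVA with no named term, estimate or interval. A usually more precise analysis is available from a baseline score already collected. With equal SDs the ANCOVA interval is 4 to 18% narrower over ρ of 0.3 to 0.7 and 18 to 36 complete pairs. With a 3-month SD 1.25 times baseline, the result runs from 10% narrower to 3% wider; with 0.8 times baseline, it is 18 to 28% narrower. These figures rest on assumed SDs and correlations, complete pairs, equal arms and normal scores. This is lost precision and underspecification, not bias or an invalid test, and the primary outcome is not affected. The plan should be changed, but the trial does not depend on it.

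**What to change.** Replace only the mixed-ANOVA sentence under Secondary analysis, for example with: *For each King's Health Questionnaire score analysed, the 3-month score will be regressed on randomised arm and the pre-randomisation value of the same score (ANCOVA); the between-arm result is the adjusted mean difference with 95% CI.* The paired t-tests can stay as they are.

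If the mixed ANOVA is preferred, name group-by-time as the term tested and report the between-arm difference in mean change with 95% CI.

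Either option is a wording change and needs no new data. ANCOVA costs one residual degree of freedom and a small penalty for estimating the slope: at worst an interval 4.1%, 2.8% or 1.7% wider in expectation (N = 18, 24, 36). Neither option deals with missing 3-month scores, which need their own rule, or says which questionnaire scores are to be analysed.
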